#### **Brief Summary:**

The goal of this study is to learn about supporting pregnant and postpartum women living with HIV with treatment adherence. The investigators will conduct a pilot study of an intervention that includes peer counseling about viral load levels and rapid delivery of viral load results. The investigators will evaluate the feasibility of the intervention, and will assess whether it improves viral suppression 6 months following the intervention, compared to historical controls.

#### **Detailed Description:**

The investigators will examine the use of more frequent virologic monitoring with enhanced communication around low-level viremia as a strategy to identify and support pregnant and postpartum women at risk of virologic failure. Virologic monitoring itself can reinforce adherence in stable patients, and more frequent monitoring can detect potential adherence challenges early. Notably, low-level viremia is a strong predictor of subsequent virologic failure, and the lowest level associated with perinatal transmission is not known.

The pilot study will run for 6 months at 4 Ministry of Health facilities in Kisumu County, Kenya; 275 participants will be enrolled. Prior to the pilot study, 125 controls will be enrolled prospectively, and 150 controls will be abstracted from records from the prior year.

### **1. INTRODUCTION/BACKGROUND**

**Emerging estimates of virologic suppression fall far short of the UNAIDS target among pregnant and postpartum women living with HIV on antiretroviral therapy (ART) in sub-Saharan Africa.** The UNAIDS 90-90-90 targets to help end the AIDS epidemic are: 90% of persons living with HIV know their status; 90% of those who know their status are on ART; 90% of those on ART are virologically suppressed. Lack of virologic suppression magnifies the risk of disease progression and sexual and perinatal transmission of the virus. The emerging estimates of viremia build on the concerning recent meta-analysis reporting 24% of pregnant women and 43% of postpartum women had suboptimal ART adherence across 51 studies, including 6 from Kenya and 5 each from South Africa and Zambia. Several studies have shown

that the vast majority of viremia experienced perinatally and otherwise is due to suboptimal adherence to ART rather than acquired resistance. Reaching the third 90 target requires a lifelong commitment to optimal ART adherence. However, pregnancy and the postpartum period introduce significant transitions in daily routines which present both unique challenges to medication adherence and unique opportunities for intervention.

**Evidence-based strategies to improve adherence and reduce viremia risk are not always optimally delivered to pregnant and postpartum women most in need of support.** For persons with or “at risk” of virologic failure, Kenyan guidelines are in place for enhanced virologic monitoring, enhanced adherence assessment and counseling, and enhanced referrals for nutrition and psychosocial support. However, strategies are needed to identify persons “at risk” of virologic failure, prior to detection of viremia or at the earliest possible time-point of non-suppression, to optimize delivery of timely enhanced support. Such services provided after virologic failure occurs may come too late to prevent the development of resistance or transmission of the virus.

**Virologic monitoring can reinforce adherence in stable patients.** With frequent monitoring, adherence challenges can be detected and addressed early. In addition, low-level viremia is a strong predictor of subsequent failure, and the level associated with perinatal transmission is not known. Thus, using a sensitive viral load assay (lower limit of detection  $\leq 100$  copies/mL) every 3 months in pregnancy and up to 6 months postpartum could provide an opportunity to provide enhanced support early.

The scientific premise of this proposal is that enhanced virologic monitoring has the potential to improve health outcomes in the highest risk patients. Early adherence support for pregnant and postpartum women most at risk of viremia could have an important impact on reaching the UNAIDS third 90 target in this population, and ultimately on improved maternal and infant outcomes among women living with HIV.

## **2. OBJECTIVES**

**Objective:** Evaluate the implementation and potential impact of risk assessment with enhanced virologic monitoring to facilitate targeted, evidence-based adherence support to pregnant/postpartum women at risk of viremia in a pilot study in western Kenya.

## **3. DESIGN AND METHODOLOGY**

The study will be conducted within MoH clinics, in Kisumu County, Kenya. Kisumu County is one of the regions of Kenya most affected by the HIV epidemic: in 2015, adult HIV prevalence (age 15-49) was 20% and the rate of perinatal transmission was 20%.

In a 6-month pilot study, we will evaluate the implementation and potential impact of enhanced virologic monitoring for pregnant and postpartum women living with HIV to reduce the risk of viremia and loss from care. Prior to the pilot study, we will sample 2 control groups: 1) 125 women will be prospectively enrolled at the pilot study sites (as part of the CAPS mobility sub-study), and 2) 150-320 women will be randomly selected from de-identified electronic medical records.

**(a) Study sites:** 2-4 clinics will be selected for the pilot study.

**(b) Study populations:** All women seeking care at these sites who are on ART **and**, either in their 3rd trimester of pregnancy, in the maternity ward for delivery, or within the first 6 months postpartum are eligible. Our rationale for this time range is: (1) Late pregnancy and delivery are critical periods for prevention of mother to child transmission. (2) 0-6 months postpartum is a period highly susceptible to disengagement from care among women living with HIV.

**(c) Sampling:** For prospectively enrolled controls and pilot study participants, to ensure adequate representation from each facility and to avoid seasonal differences by site, we will conduct recruitment at each site simultaneously, visiting each site within any given week in which recruitment is done, to the best of our ability. We will invite all women attending clinic on days of recruitment at each site, and will trace all women late for visits that were due on those recruitment days. Controls selected from records only will be randomly sampled from eligible women with viral loads scheduled for collection in the 6 months prior to the pilot study.

Recruitment.

Building on our established relationships with MoH and clinic leadership in Kisumu, we will work collaboratively with these teams to ensure on-site research staff support with patient recruitment, including access to patients, clinic records, and registers. We will attempt to recruit, consent, enroll, and conduct baseline visits in conjunction with a clinic visit to reduce the burden on participants. For participants that prefer to meet elsewhere, we will arrange a separate time and place to meet at their convenience. For those who are late for visits, mentor mothers will use all available phone numbers and location data in the clinical record to locate the individual. For participants who are hard to reach, we will train mentor mothers with established tracking methods to determine potential relocation information about the participant.

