#### **4. DATA MANAGEMENT**

Analyses of implementation outcomes. Analyses will summarize acceptability and feasibility survey results, summaries of adoption, as well as the clinical and sociodemographic characteristics of the women seen at the clinic during the pilot study, using descriptive statistics.

Evaluating the potential impact on maternal viremia. The frequency of viremia in the year preceding the pilot to the frequency among women seeking care during the pilot will be

compared with logistic regression, adjusted for baseline differences in clinical and demographic characteristics.

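### Clinic is not in the impact model and does not govern the draw of records controls, so a difference in clinic mix between groups can bias the viremia contrast in either direction

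*Combined protocol and SAP*

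**What the plan says.** **Groups and sites.** The Detailed Description says "The pilot study will run for 6 months at 4 Ministry of Health facilities in Kisumu County, Kenya; 275 participants will be enrolled". Section 3(a) is looser: "2-4 clinics will be selected for the pilot study". There are two control groups. For the first, "125 women will be prospectively enrolled at the pilot study sites". For the second, section 3 says "150-320 women will be randomly selected from de-identified electronic medical records", while the Detailed Description gives the lower figure only: "150 controls will be abstracted from records from the prior year".

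**How site is handled in recruitment.** For the prospective controls and the pilot women, section 3(c) schedules recruitment at all sites in parallel, "to ensure adequate representation from each facility and to avoid seasonal differences by site". All women attending on a recruitment day are invited, and those late for visits due that day are traced. For the other group the rule is: "Controls selected from records only will be randomly sampled from eligible women with viral loads scheduled for collection" in the six months before the pilot. It contains no stratification, quota or matching by clinic.

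**How site is handled in the analysis.** Section 4 compares viremia before and during the pilot by logistic regression, "adjusted for baseline differences in clinical and demographic characteristics". The confounders listed under Baseline characteristics in section 3 are individual and social: sociodemographic and health information, clinical record data, food insecurity, stress and depression. Clinic appears in neither place, and clustering by site is not mentioned.

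**The concern.** The plan treats site as worth managing for two of its three groups, then leaves it out of the third and out of the model. The two mechanisms need not give the same clinic mix. A random draw from records follows the number of eligible records at each clinic. Prospective enrolment follows how many recruitment days each site gets, who attends on those days and who consents.

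The outcome is a routine-care viral load, and viremia means any detectable level, so how each clinic delivers care can bear on it. Records controls are also most of the comparator: 150 of 275 controls (55%), or 320 of 445 (72%). They have no study visit, whereas sociodemographic and mobility data are to be collected from participants directly. Individual covariates may therefore be thin for them, and cannot be relied on to stand in for clinic.

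At stake is the estimate of potential impact that is meant to inform later research. A contrast produced by clinic mix would look the same as a benefit or a harm of the intervention.

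**Working it through.** The documents state no viremia rate, effect size, alpha, power or per-clinic volume, so there is no figure of the plan's to reproduce. The check is an illustration under no intervention effect.

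**Inputs from the documents.** Pilot women 275; prospective controls 125; records controls 150 to 320; 2 to 4 clinics. Total controls: 125 + 150 = 275, or 125 + 320 = 445.

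**Assumptions (none from the documents).** Four clinics with viremia of 10, 15, 20 and 25%. Pilot women and prospective controls spread equally over them. Records controls spread 40/30/20/10%, or the reverse.

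**Step 1: group rates.** Group rate = sum of (clinic share × clinic rate).
- Pilot and prospective controls: 0.25 × (10 + 15 + 20 + 25) = 17.5%
- Records, 40/30/20/10: 4.0 + 4.5 + 4.0 + 2.5 = 15.0%
- Records, 10/20/30/40: 1.0 + 3.0 + 6.0 + 10.0 = 20.0%

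Against records controls alone, the spurious gap is 2.5 points either way.

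**Step 2: pool all controls.** Section 4 does not say whether the two control groups are pooled. If they are, the rate is (125 × 17.5% + n × records rate) / (125 + n). The false-positive rate is the two-sided 5% rejection probability of the two-proportion test with 275 pilot women.

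| Records mix | Records controls | Pooled control rate | Gap (pilot minus control) | Odds ratio | False-positive rate |
|---|---|---|---|---|---|
| 40/30/20/10 | 150 | 16.1% | +1.4 points | 1.10 | 7% |
| 40/30/20/10 | 320 | 15.7% | +1.8 points | 1.14 | 10% |
| 10/20/30/40 | 150 | 18.9% | −1.4 points | 0.91 | 7% |
| 10/20/30/40 | 320 | 19.3% | −1.8 points | 0.89 | 9% |

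The dilution is the records share of the controls: 2.5 × 150/275 = 1.4 and 2.5 × 320/445 = 1.8. More records controls means more bias.

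**Step 3: range of assumptions.**
- Equal rates at every clinic: odds ratio 1.00 and 5% false positives, whatever the mix.
- A steeper case, with rates 30/20/15/10% and records mix 55/25/12/8%: pilot rate 18.75%, records rate 24.1%. The pooled odds ratio is 0.83 with 14% false positives (150 records controls), or 0.79 with 23% (320).

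**Step 4: add clinic to the model.** In the steeper case, 600 simulated trials per setting with clinic indicators gave average odds ratios of 0.99 and 1.01, with 5.5% rejection in both. Over all 16 settings simulated (four sets of clinic rates, two records mixes, two sizes), the odds ratio with clinic indicators was 0.99 to 1.01 and rejection 4.5 to 6.5%. None of these settings stratified the records draw.

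**The case against.** The strongest reply has four parts.

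1. **Sampling frame.** A reader might infer that records controls could come from clinics outside the pilot. The documents do not support that. Section 3(c) samples eligible women, and section 3(b) ties eligibility to women seeking care at the selected sites. The frame is by implication the pilot clinics. What stands is that the plan does not say so outright and does not control the mix among those clinics.

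2. **Balance in the prospective groups.** A reader might infer that pilot women are balanced equally over clinics while records controls follow volume. The plan promises adequate representation, with no quotas, and invites everyone attending on recruitment days. Busier clinics would therefore contribute more women in both schemes. The mixes may turn out similar, and the equal pilot mix used above is only an assumption. They can still diverge through recruitment days, attendance and consent, and nothing in the plan prevents or corrects that.

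3. **Stakes.** The end of section 3 says that the pre-post comparison is not causal and that differences may have temporal or other causes. This lowers the stakes. It is a fair caveat for what the design cannot remove, but clinic mix can be removed.

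4. **Open covariate list.** The wording in section 4 does not exclude clinic. True, but nothing commits to it, and if the de-identified extract does not keep the facility, it could not be added later.

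**Conclusion.** The point holds as a modest, avoidable weakness in an exploratory comparison. As written, the plan has no clinic term and no control of clinic mix among the controls who form the majority of the comparator. Bias needs two conditions: the mix differs between groups, and viremia differs between clinics. If either fails there is none.

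Its size and sign cannot be derived from the documents. Under the main illustration it is 2.5 points against records controls alone and 1.4 to 1.8 points if controls are pooled. The 2.5 points should not be read as the expected bias of the planned analysis: that figure leaves out the 125 prospective controls, who are recruited by the same site scheme as the pilot women, and it assumes that clinic volume is ranked exactly with (or against) viremia. The larger false-positive rates come from steeper assumed differences. The case for a clinic term does not depend on which illustration is nearest the truth, since it removed the bias in every setting tried.

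**What to change.** - State in section 3(c) that records controls are drawn from the pilot clinics.
- Require the de-identified extract to carry the clinic for each woman, and record clinic for the other two groups.
- In section 4, include clinic as a fixed effect in every impact model: 1 indicator for 2 clinics, up to 3 for 4. With so few clinics, indicators are preferable to random effects or cluster-robust errors.
- Report the clinic distribution of each group.
- Reconcile the number of sites (4 or 2–4) and of records controls (150 or 150–320), since both affect this model.

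Stratifying the records draw by clinic is optional. Both control groups are sampled before the pilot, so strata cannot follow actual pilot enrolment. They would have to use planned enrolment or the clinic distribution of the prospective controls.

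The cost is a few sentences, one field in the extract and 1 to 3 degrees of freedom. Clinic terms do not remove the calendar-time confounding that the protocol acknowledges, so its non-causal caveat should stay.

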### 1) More frequent viral load collection

Our research assistants will be trained in phlebotomy. All participants who have not had a viral load collected within the prior 80 days will have a blood sample collected at baseline for viral load testing. Those who enroll in the first 3 months of the pilot study period will be eligible for a follow-up visit within the 6-month pilot study period, and will have viral load assessed again at the 3-month follow up visit.

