### 3) Enhanced viral load counselling

Mentor mothers will reinforce adherence with all patients with undetectable levels via scripted messaging to reward and encourage healthy behavior. For those with any detectable levels, mentor mothers will be trained to provide targeted counseling about low-level and higher viral loads. Women who report significant psychosocial barriers will be referred to a social worker.

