### HIV care outcomes.

The viral loads collected as part of the intervention will guide the counselling that is provided during the study. Study outcome viral loads will be routine care viral loads that are collected (1) within the 6 months following the control participants enrollment (and only) study visit, for prospectively enrolled controls, (2) within the 6 months prior to the pilot study for controls

retrieved from electronic records, and (3) within the 6 months following the pilot participants last study visit. The study team will work together with the clinical teams to ensure these viral load outcomes are measured and recorded according to national guidelines. Viremia will be defined as any detectable levels of HIV RNA. Suboptimal care engagement will be defined as late for a clinic visit by 30 days or more.

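### Unequal outcome windows let time on ART at the outcome test differ between pilot women and controls, and adjusting for baseline characteristics does not remove this

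*Combined protocol and SAP*

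**What the plan says.** - Eligibility (section 3, Study populations): "All women seeking care at these sites who are on ART" and who are in the third trimester, at delivery, or up to six months postpartum. No minimum time on ART is set here or elsewhere.
- Outcome (HIV care outcomes): "Viremia will be defined as any detectable levels of HIV RNA". The outcome tests are routine-care viral loads taken on the national schedule, which the documents do not reproduce.
- Outcome windows (same section): for prospective controls, "within the 6 months following the control participants enrollment (and only) study visit"; for records controls, "within the 6 months prior to the pilot study for controls"; for pilot women, the six months that begin at their final study visit.
- Pilot visits (More frequent viral load collection): women enrolled in the first three months "will have viral load assessed again at the 3-month follow up visit". Their outcome window therefore opens three months after enrolment. For other pilot women it opens at enrolment.
- Analysis (section 4): logistic regression adjusted for baseline clinical and demographic differences. No covariate is named. HIV history is to be abstracted from records (Baseline characteristics), but ART start date is not mentioned.

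**The concern.** A woman who has just started ART can still be detectable because she has had little time on treatment. If the chance of being detectable falls with time since starting, the group tested later on ART shows less viremia whatever counselling it received.

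The window definitions make such a difference plausible. A pilot woman with a follow-up visit has at least three more months on ART before her window opens. A prospective control can be tested straight after enrolment. A records control has no enrolment date, so her test can fall at any time on ART, including early.

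Adjusting for ART duration at baseline would not solve this. Two women with the same duration at enrolment still differ at the outcome test if one is tested three months later. Records controls have no study visit at all, so their baseline is undefined. What is at stake is how the impact comparison is read when it is used to inform later research.

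**Working it through.** The plan gives no expected viremia rate, effect size or power figure, so there is nothing of its own to reproduce. The calculation below assumes no intervention effect.

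**Inputs from the documents.** 125 prospective controls and 150 records controls (Detailed Description); the outcome windows; the three-month visit for early enrollees only.

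**Assumptions.**
- Recent starters make up 15% of every group.
- 50% of them are detectable if tested within 3 months of starting, and 20% if tested later.
- They have been on ART 0–3 months at enrolment, spread uniformly.
- Tests are uniform over the six-month window.
- Half of pilot women have the three-month visit.
- Viremia in established women is the same in all groups, so it cancels from every difference.

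**Step 1, prospective controls.** A recent starter is tested within 3 months of starting if months on ART at enrolment plus delay to the test is below 3. The probability is (3 × 3 / 2) / (3 × 6) = 4.5 / 18 = 25%. Viremia among recent starters is 0.25 × 50% + 0.75 × 20% = 27.5%.

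**Step 2, pilot.** With a three-month visit, every test falls after 3 months on ART: 20%. Without one, timing matches prospective controls: 27.5%. The average is 0.5 × 20% + 0.5 × 27.5% = 23.75%.

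**Step 3, pilot against prospective controls.** 0.15 × (27.5 − 23.75) = 0.56, about 0.6 points. If every pilot recent starter had the three-month visit: 0.15 × (27.5 − 20) = 1.1 points.

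**Step 4, pilot against pooled controls.** The timing of records controls is unknown, so both ends are shown.
- All recent starters among records controls tested within 3 months of starting (50%): pooled (125 × 27.5 + 150 × 50) / 275 = 39.77%. Difference: 0.15 × (39.77 − 23.75) = 2.4 points.
- All tested later (20%): pooled (125 × 27.5 + 150 × 20) / 275 = 23.41%. Difference: 0.15 × (23.41 − 23.75) = −0.05, essentially zero.
- Section 3 allows up to 320 records controls. The early end then becomes (125 × 27.5 + 320 × 50) / 445 = 43.68%, and 0.15 × (43.68 − 23.75) = 3.0 points.

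**Step 5, share of recent starters (125 + 150 controls).**

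| Share | Against prospective controls | Against pooled controls, records all early |
|---|---|---|
| 5% | 0.05 × 3.75 = 0.2 | 0.05 × 16.02 = 0.8 |
| 15% | 0.6 | 2.4 |
| 25% | 0.25 × 3.75 = 0.9 | 0.25 × 16.02 = 4.0 |

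**Cross-check with a smooth decline.** Let the chance of being detectable t months after starting be 0.15 + 0.85 × exp(−t × ln2 / m), with m = 1, 2 or 3 months, 15% viremia in established women, the same visit timing, and records controls tested at the moment of eligibility (the least favourable reading). The pooled difference is 0.9–1.2 points at a 5% share, 1.9–2.4 at 10% and 3.7–4.8 at 20%. For example, at m = 2 recent-starter viremia is 30.0% in the pilot, 37.3% in prospective controls and 67.8% in records controls. The pooled control figure is 53.9%, and 0.20 × (53.9 − 30.0) = 4.8. Against prospective controls alone the odds ratio stays between 0.87 and 0.99 over shares of 5–30%.

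In both calculations, equal timing with equal shares gives a difference of zero.

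**The case against.** The strongest reply is that open eligibility is not itself a source of bias. The analysis compares groups, and viremia in recent starters declines among controls too. That stands: a reader might infer that admitting women with any time on ART is enough to mimic an intervention effect, but the zero result under equal timing and equal shares shows otherwise. The problem arises only through the unequal windows.

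A reader might also infer that the plan labels all viremia as adherence-related. The Introduction does say that the "vast majority of viremia experienced perinatally and otherwise is due to suboptimal adherence to ART rather than acquired resistance", but that is background and contrasts adherence with resistance. The outcome is defined simply as viremia, and counting all of it is legitimate because the Introduction ties lack of suppression itself to transmission risk.

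Two further replies stand in part. First, the routine testing schedule might keep very early tests out of the outcome. The documents do not give that schedule, so this can be neither relied on nor excluded. Second, section 3 already states that the pre-post comparison is not causal and could reflect temporal factors, and HIV history is collected with confounding in mind. The disclaimer limits the weight placed on the result. It does not remove a difference that one extracted date would let the analyst address. Baseline ART duration could handle unequal shares of recent starters, but not the later test in the pilot.

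**Conclusion.** The concern holds in a limited form. Time on ART at the outcome test can differ by group, probably in the pilot's favour, and the planned baseline adjustment leaves that difference in place. Under the 15%, 50% and 20% assumptions the spurious difference is about 0.6 points against prospective controls. Against 125 + 150 pooled controls it runs from about zero to 2.4 points, depending on when records controls are tested. Most of the possible bias therefore comes from the records controls.

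A larger figure is tempting: 0.15 × (50 − 20) = 4.5 points. It needs every recently started control to be tested early and every recently started pilot woman late. The plan's windows do not support that, because prospective controls have a full six months and only early pilot enrollees have the later window. The true size cannot be found from the documents, since the share of recent starters, the speed of suppression and the routine schedule are all missing.

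**What to change.** 1. Extract ART start date in all three groups, together with the date of the outcome viral load.
2. In section 4, name time on ART at the outcome viral load as a term in the logistic model, modelled flexibly (for example with a spline) because the decline is unlikely to be linear.
3. Tabulate time on ART at the outcome test by group, so that any imbalance is visible.
4. Add a sensitivity analysis that excludes outcome tests drawn soon after ART start, with the cut-off fixed before the data are examined. It should remain a sensitivity analysis: pilot women with later tests pass any cut-off more often than comparable controls, so the exclusion itself selects differently by group.

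Eligibility, recruitment and care are unchanged. The cost is one more extracted field, one more model term and a slightly wider confidence interval. Without the start date, the share of recent starters cannot be reported and the size of the problem cannot be checked afterwards.
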